Total knee arthroplasty (TKA) is among the most common surgical procedures performed in the US^{1,2}, and as the population ages and face age-related joint deterioration, will only increase in frequency.^{3,4} Although in the majority of cases, patient-centered outcomes (pain, function and quality of life) are improved following this procedure, a significant number of patients develop chronic post-surgical pain (CPSP), which is often rated as severe, and includes treatment-resistant neuropathic components.⁵ The International Association for the Study of Pain defines CPSP as pain that develops or increases in intensity after a surgical procedure, persists beyond the tissue healing process (> 3months), and is localized to the surgical field or innervation territory of nerve located in surgical field.²⁴ Rates of CPSP are alarmingly high following TKA, with Petersen and colleagues^{6,7} reporting that between 44% to 53% patients develop CPSP, 15% to 19% of whom rate their pain as severe. Clearly, the development of CPSP following TKA is a significant adverse outcome, which brings with it decreased quality of life, diminished functionality, disability, and perhaps most concerning in the era of the opioid crisis, long-term opioid use.^{8,12} Further, CPSP is associated with notable economic burden, with recent analysis suggesting almost \$30,000 in annual adjusted indirect costs to patients per year, an amount directly related to the severity of CPSP pain.¹³

Preoperative Predictors of Chronic Post-surgical Pain

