A power analysis was conducted for the post-operative pain outcomes; being a novel intervention, opioid taper outcomes were not considered. Estimated group means, variances, and effect-size were drawn from the literature.^{41,42} The sample size estimate was derived for the primary outcome variable, chronic pain severity, using an expected baseline mean of 4.82 (Effect size: 0.33). Based on estimates obtained, a sample size of 75 participants provides 80% power to detect a pre-post improvement in pain severity (14.5%), depression (21.3%), anxiety (24.3%), and catastrophizing (29.5%), statistically significant at alpha of 0.05. Being a novel intervention, the analysis for chronic post-surgical pain will be considered exploratory and used to obtain effect size estimates. We anticipate a low attrition rate (10%) and will over-recruit 16 additional participants (total 83 subjects per group) to retain adequate power.

2. Key Inclusion Criteria:

[figure not shown]

Figure 1. Predictive factors of CPSP following TKA

1. Males and females, age > 21 years
2. Chronic non-malignant pain of at least 3 months duration
3. Morphine equivalent daily dose (MEDD) > 50 milligrams for at least 3 months
4. Able to enroll at least 4 weeks prior to planned surgery
5. Able to speak, read and comprehend in English at the 6th grade or higher proficiency

Participants will be selected so as to represent the gender, ethnicity, and age of the patient population of individuals seeking TKA in greater Philadelphia area, thus the sample is expected to be 50% women, 55% white, 35% African-American, 6-8% Latino, and 2-4% other or multiracial, and on average 67 years of age. No restrictions on gender or ethnicity will be applied. Because total knee arthroplasty surgery is uncommon in children, individuals under the age of 21 will not be included in this proposed study.

3. Key Exclusion Criteria:

1. Pain of malignant origin
2. Current or past history of opioid use disorder (including those on medication-assisted therapy)
3. Revision of TKA
4. Comorbid CNS disease such as dementia, HIV, psychosis, poorly controlled bipolar disorder or any condition interfering with informed consent

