The research will be conducted in the Department of Orthopaedic Surgery at Penn Presbyterian Medical Center, and data analysis will be performed at the Biostatistics * Evaluation * Collaboration * Consultation * Analysis (BECCA) lab at the U Penn School of Nursing.

The duration of subject participation is approximately seven (7) months beginning four (4) weeks prior to surgery and ending following the 6-month data collection time point. The baseline study session will last approximately 30minutes for those in the control group and 60minutes for those in the experimental group. For those in the experimental group, subjects will spend approximately nine (9) hours prior to surgery receiving the intervention. For those in the control group, subjects will spend approximately four (4) hours prior to surgery receiving the standard educational care. Just prior to the surgery, subjects in both groups spend approximately 45minutes providing pre-operative data, and they will additionally spend one (1) hour providing data at the 3- and 6-month follow up at 30minutes each. Thus, the duration of participation for those in the experimental group is approximately 12 hours, and for those in the control group, approximately 7.5 hours.

METHODS:

1. Study Instruments:

Preoperative chronic pain – The severity of preoperative chronic pain will be evaluated with the Brief Pain Inventory (BPI),⁵² along two dimensions: intensity and interference. Pain intensity is rated on a 0 (no pain) to 10 (worst pain imaginable) scale as the worst in the past 24 hours, least in the past 24 hours, average pain and current pain. Pain interference is measured in 7 areas: general activity, mood, walking ability, work, sleep, enjoyment of life and relationships on a 0 (no interference) to 10 (interferes completely) scale. The composite mean of these scores are used as a pain interference score. BPI scores will be collected prior to the intervention and compared to those collected just prior to surgery and at 3- and 6-month follow-up.

Long-term opioid use – Preoperative opioid use will be measured by converting to morphine equivalent daily dose (MEDD) prior to beginning the intervention, during the study visit just prior to surgery and at the 3 and 6 months follow up if the patients are still taking opioids. At each timepoint, state prescription drug monitoring program will be queried as a check on self-reported opioid use.

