Chronic post-surgical pain – To evaluate for the presence of CPSP, subjects will be asked at 3- and 6-months if they have pain in the surgical site that developed or increased in intensity following the surgery utilizing a checklist based upon the IASP definition of CPSP (Appendix). If they respond affirmatively, BPI pain scores will be collected to assess the intensity and interference associated with the CPSP. In addition, subjects will be asked if they are continuing to use opioids at these timepoints, and if so, daily MEDD calculated for analysis.

2. Group Modifications:

The only group modification with respect to measures is that only those in the intervention group will participate in the survey assessing subject satisfaction with the intervention.

3. Method for Assigning Subjects to Groups:

A randomization scheme will be generated by the study biostatistician and provided to the study coordinator who will assign consecutively enrolled subjects to group.

4. Administration of Surveys and/or Process:

The data collection schedule is described below:

	Baseline (T-4weeks)	Pre-operation (T0)	Post-operation (T = 72hr)	Follow-up (T + 3 and 6 months)
Chronic Pain Intensity (BPI)	X	X		X
Opioid Use (MEDD)	X	X		X
PDMP review	X			X
Pain Catastrophizing (PCS)	X	X		X
Depression & Anxiety symptoms (PROMIS)	X	X		X
CBT use, adherence, satisfaction ^a		X		
Post-operative Pain Severity (72hr VAS)			X	
Post-operative Pain Severity (72hr MEDD)			X	
Chronic post-surgical pain checklist				X

^a subjects in treatment group only

5. Data Management:

Collected data will be entered into the U Penn School of Nursing REDCap (Research Electronic Data Capture) system by trained CITI- and HIPAA-certified research assistants, which is a central and secure resource for data processing and management. As the front-end collection instrument is created, REDCap automatically creates a database designed to store the data that will be recorded from the research. The U Penn School of Nursing has licensed its own version of REDCap that is housed on password protected servers located within a data center inside the School of Nursing firewall, and therefore are afforded the same network protections as other sensitive clinical systems. REDCap was developed specifically around HIPAA-Security guidelines with features such as data encryption and is recommended to Penn researchers by our Office of Human Research.

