Data quality will be monitored by random inspection of the completed datasets by the study coordinator and any problems detected will be discussed with the co-PIs. In addition, the PIs will carefully monitor the data accrual weekly. Data will be entered on an ongoing basis under the direction of the study coordinator, and weekly reports detailing health events, study progress, and data accuracy and completeness will be generated for review by the PIs and co-investigators. Quality assurance activities will be supervised by the study coordinator. Prior to analysis, missing data or discrepancies will be corrected by the project director based on source documents. The study's statistician will analyze the data, using SAS for Windows Version 9.4 statistical software.

Data monitoring of all aspects of this study will proceed in an exacting manner and meet all IRB requirements. Data will be collected by trained research staff using standardized hardcopy and electronic forms and will only be identified with a study ID. Personal identifiers required for follow-up will be linked with the study ID and kept confidential by Drs. [name] and [name] in a secured cabinet. No presentation or publication of the results of this study will refer to the individual participants or present information that would identify any participant. No data will be disclosed to personnel not listed on the study protocol.

6. Subject Follow-up:

Using contact information obtained at the baseline visit, subjects will be contacted via telephone at 3- and 6-months following surgery to determine if CPSP is present utilizing a checklist based upon the IASP definition of CPSP (Appendix). If present, the BPI will be administered, and any opioid use recorded and checked against the PDMP. In addition, the PCS and PROMIS measures will be collected to evaluate the durability of CBT training effects. The sample does not include transient groups, minimizing potential attrition.

STUDY PROCEDURES:

1. Detailed Description:

The study procedures, including all the visits, contacts, and interactions are described sequentially below:

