Appendix
Chronic Post-Surgical Pain (CPSP) Checklist

If Brief Pain Inventory indicates that patient still has pain:	
1. Did the pain develop or increase in intensity after the surgical procedure?	 YES  NO
2. Is the pain in the same location/area as the surgical procedure?	 YES  NO
3. Is the pain distinct from other kinds of pain that were present prior to the surgery?	 YES  NO  NA
4. Could your pain be described as burning, prickly, tingling, electric shocks and/or pins and needles?	 YES  NO
5. Is the skin covering your painful area more sensitive to touch?	 YES  NO

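### The plan gives conflicting rules for the 3- and 6-month BPI: several sections give it only to patients with CPSP, others to everyone, and none says which governs

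*Combined protocol and SAP*

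**What the plan says.** Three places make the follow-up BPI depend on CPSP. Methods, 1. Study Instruments (Chronic post-surgical pain) first asks about pain at the surgical site and continues: "If they respond affirmatively, BPI pain scores will be collected to assess the intensity and interference associated with the CPSP". Methods, 6. Subject Follow-up, and Study Procedures, 1. Detailed Description (Chronic Post-surgical Pain), both say: "If present, the BPI will be administered, and any opioid use recorded and checked against the PDMP".

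Two places collect it without condition. Methods, 1. Study Instruments (Preoperative chronic pain) says: "BPI scores will be collected prior to the intervention and compared to those collected just prior to surgery and at 3- and 6-month follow-up". In the schedule under Methods, 4. Administration of Surveys and/or Process, the row that begins "Chronic Pain Intensity (BPI" is marked at follow-up. The table's only footnote limits a different row to the treatment group.

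The Appendix reverses the order. The CPSP checklist opens with "If Brief Pain Inventory indicates that patient still has pain", so the BPI has to come first.

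Study Procedures, 5. Statistical Analysis fits a mixed model that includes months 3 and 6 and reports mean change from baseline by group at each time point. It does not mention BPI scores that are absent by design. On the status of the CPSP analysis, Target Population and Accrual says that "the analysis for chronic post-surgical pain will be considered exploratory and used to obtain effect size estimates".

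**The concern.** The conditional wording sits in the sections that tell staff how to run the telephone contact, so it could well be the rule that is followed. A BPI not taken at the contact cannot be recovered later.

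CPSP status arises after randomization and is an outcome the intervention is meant to improve. If only CPSP-positive patients have a BPI, an arm comparison of that score, or of its change from baseline, sets one selected group against another and is no longer a randomized comparison. The plan's stated main goal is reliable effect sizes for larger studies, and a selected estimate would not serve that goal.

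**Working it through.** **1. The plan's own sample-size figure.** Target Population and Accrual gives an effect size of 0.33, alpha 0.05 and 75 participants for 80% power on a pre-post change. A paired t-test (two-sided alpha assumed) with n = 75 and d = 0.33 has 80.5% power, so the figure reproduces. It is a within-group calculation for the pre-operative period and uses no follow-up BPI. The present point leaves it untouched.

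**2. Can a CPSP-negative patient be given a score of zero?** The Background defines CPSP as "pain that develops or increases in intensity after a surgical procedure", and item 1 of the checklist asks the same thing. Inclusion criterion 2 requires "Chronic non-malignant pain of at least 3 months duration". A patient whose knee pain is unchanged, or reduced but still present, answers no to item 1 and is CPSP-negative with a BPI above zero. Zero is therefore not a valid substitute.

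**3. Can the analysis model fill the gap?** Under the conditional rule, no CPSP-negative patient has an observed BPI at that visit. A mixed model or an imputation would have to extrapolate to that group from CPSP-positive patients and from other times, on an assumption the data at that visit cannot check.

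**4. How many scores are lost at one visit?** Inputs: 150 patients, 75 per arm (Study Design; the 166 enrolled allow for 10% attrition), and CPSP rate p. The Background cites 44% to 53% for TKA patients; the other rates are assumed.

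- Patients without a BPI = 150 × (1 − p)
- Scores left per arm = 75 × p, taking the same rate in both arms
- Width of the confidence interval for an arm difference, relative to complete collection = √(1/p), taking the same SD

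| CPSP rate p | Without BPI, of 150 | Scores per arm | CI width factor |
|---|---|---|---|
| 30% (assumed) | 105 | 22.5 | 1.83 |
| 44% (cited) | 84 | 33 | 1.51 |
| 53% (cited) | 70.5 | 39.75 | 1.37 |
| 60% (assumed) | 60 | 45 | 1.29 |
| 70% (assumed) | 45 | 52.5 | 1.20 |

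The higher rates are plausible here. The section on preoperative predictors names prior pain and chronic opioid use as risk factors for CPSP, and the inclusion criteria require both of every patient.

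**5. How many have no score at either visit?** If CPSP status is the same at 3 and 6 months, the share is 1 − p, or 47-56% at the cited rates. If status at the two visits were independent (the lower extreme), it is (1 − p)²: 0.47² = 22% to 0.56² = 31%.

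**6. When must it be settled?** Enrollment starts in month 3, surgery follows about 4 weeks later, and the first contact comes 3 months after that: 3 + 1 + 3 = about study month 7.

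**The case against.** The strongest reply is that little depends on the follow-up BPI. Objective 3, the Study Design section and the Objective 3 analysis name 72-hour pain and CPSP rates. The sentence comparing BPI over time stands under preoperative pain and names no arm contrast. The conditional BPI has a descriptive purpose of its own, to characterize the pain of CPSP cases. The CPSP analysis is exploratory. All of this stands, and it limits the point to one secondary measure. It does not remove the conflict: the plan still promises a BPI comparison that reaches 6 months, and the change-from-baseline summary can be read to include it.

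A reader might infer that the two orders lock each other, since the BPI waits for the checklist and the checklist waits for the BPI, so that CPSP rates are lost as well. The documents do not support that. Staff who follow either order complete the checklist wherever it applies, and under the Appendix order the BPI simply comes first. CPSP rates are unaffected provided the checklist is completed.

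A reader might also infer that half the patients would have no follow-up BPI at all. The figure is per visit, rests on rates cited for other TKA patients, and falls if CPSP status changes between visits or if CPSP is more common in this sample.

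Finally, the quoted sentence might be taken to restrict opioid recording to CPSP cases too. It is only ambiguous on this. The opioid paragraph, the CPSP paragraph and the schedule all cover follow-up opioid use outside the CPSP condition.

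**Conclusion.** The conflict is real and should be resolved; it affects one outcome. If the conditional wording is followed, every CPSP-negative patient lacks a BPI at that visit, and any follow-up BPI comparison or change from baseline is confined to patients selected after randomization. At the cited CPSP rates about 70-84 of 150 patients lack a score at a given visit, leaving 33-40 per arm and an interval 1.37-1.51 times as wide, apart from selection. These figures assume that the cited rates carry over to this sample, that both arms have the same rate, and that the SD is unchanged. The selection problem itself does not depend on the rate, as long as some patients are CPSP-negative.

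It would go too far to say that the bias favors one arm, since the documents determine neither its direction nor its size. Nor is the trial's main result at risk: the powered pre-operative outcome, 72-hour pain, PCS and PROMIS do not depend on this rule.

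**What to change.** In the CPSP paragraph of Study Instruments, in Subject Follow-up and in the Chronic Post-surgical Pain paragraph of Study Procedures, replace the conditional sentence with one along these lines: *At 3 and 6 months every subject contacted completes the BPI, before and regardless of the CPSP checklist; opioid use is recorded and checked against the PDMP for every subject contacted.* This agrees with the BPI and opioid paragraphs, the schedule and the Appendix.

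In Statistical Analysis, add that any between-arm comparison of follow-up BPI uses all randomized patients with follow-up data, analysed as randomized, and that BPI among CPSP cases is descriptive only. The words about follow-up data are needed because the plan expects 10% attrition and removes control patients who ask for the enhanced treatment.

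The cost is a few more minutes in a contact already budgeted at 30 minutes, a wording change in three places and a short addition to the analysis section. The collection rule has to be in place before the first 3-month contact.

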COVER PAGE

Pre-op Cognitive Behavior Therapy to Decrease Chronic Post-Surgical Pain in TKA

NCT04814992

November 23, 2020

PRINCIPAL INVESTIGATORS: [name] & [name], PhD, FAAN

PROTOCOL TITLE: Pre-op CBT to Reduce the Risk for Development of Chronic Post-surgical Pain in Patients undergoing Total Knee Arthroplasty

INTRODUCTION AND PURPOSE:

A significant number of patients develop chronic post-surgical pain following knee joint replacement surgery, and the risk factors for this problematic outcome have been identified. Proposed is the development and preliminary efficacy testing of a novel computer-assisted cognitive behavioral intervention integrating opioid taper delivered in the four weeks prior to surgery to address these risk factors, with the expectation that both the severity of post-operative pain and the subsequent incidence of chronic post-surgical pain will be reduced. In that chronic post-surgical pain brings with it diminished functionality and quality of life, ongoing opioid use, and direct patient costs, it is critical that interventions aimed at mitigating its development are implemented and evaluated in the clinical setting.

OBJECTIVES:

In a sample of adult men and women with chronic pain, on opioid therapy and undergoing a planned TKA, the objectives of this randomized clinical trial are to:

1. Add a motivational interviewing component to a validated computer-assisted CBT intervention for chronic pain (PAINTrainer) to encourage opioid tapering in the 4 weeks prior to surgery.
2. Describe the efficacy of the 4-week targeted pre-operative CBT intervention in 75 TKA patients to decrease preoperative chronic pain severity, preoperative opioid consumption, and symptoms of depression, anxiety and pain catastrophizing prior to surgery in comparison to 75 TKA patients randomized to treatment-as-usual.
3. Describe the effects of a 4-week targeted pre-operative CBT intervention in 75 TKA patients on 72hr post-operative pain severity, and 3- and 6-month rates of CPSP in comparison to 75 TKA patients randomized to treatment-as-usual.

BACKGROUND:

Knee Joint Replacement and Chronic Post-surgical Pain

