STUDY DESIGN:

A randomized clinical trial is proposed to evaluate the efficacy of the novel computer-assisted preoperative CBT/opioid sparing intervention to affect acute and chronic post-operative pain outcomes. Specifically, 150 male and female patients meeting study inclusion criteria and preparing to undergo TKA at the Penn Presbyterian Medical Center will be randomized to either receive the computer-assisted preoperative CBT intervention (n=75) or treatment-as-usual (control, n=75). The effectiveness of the intervention to address the preoperative risk factors for CPSP will be evaluated by comparing pain severity, opioid use, symptoms of depression, anxiety and pain catastrophizing before and following the 4-week pre-surgical period and compared within and across subjects. Post-operative pain severity will be abstracted from the electronic health record (EHR) and compared to post-operative pain severity ratings between the intervention and control groups. Similarly, group differences will be inspected for rates of CPSP at 3- and 6-months following surgery. In addition, due to the novelty of the CBT/opioid sparing intervention, brief (15-20min) qualitative interviews will be conducted with the participants who received it during the study visit immediately prior to surgery, to assess patient utilization, and satisfaction with the program in general, and the opioid taper component specifically; adherence is tracked by the PAINTrainer. Participants will be prompted to comment on the perceived ease of use, burden, helpfulness and quality of the CBT intervention.

A randomized clinical trial was designed because it provides the highest level of evidence and lowest risk for bias. The methods employed are predominantly quantitative, although a qualitative survey approach is used to assess subject satisfaction with the intervention. The project is designed, staffed and budgeted to be completed in 24 months. In consultation with consultants, [name] will train the study coordinator coach on delivering the opioid taper intervention during months 1-3, during which time study start-up activities will take place. Enrollment will begin month 3; at a rate of 12-13 enrollments per month, we anticipate having enrolled 166 subjects (n=150, assuming 10% attrition) by study month 15, providing adequate time for 3- and 6-month follow up, and dissemination activities.

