Pre-operative study session: Immediately prior to the surgical procedure, patients in the experimental group will meet with the study coordinator and baseline assessments will be repeated. In addition, the subject will be interviewed to gain understanding of their perceived ease, burden, satisfaction and likability of the intervention. It is anticipated that this study session will last no longer than 45 minutes. At the completion of the session, use data from the computer-assisted CBT program will be downloaded and recorded.

Post-operative Pain: Post-operative pain intensity and opioid use (converted to MEDD) data will be extracted from the EHR for the first 72 hours post-operatively. If the patient is discharged prior to 72 hours, he or she will be provided a pain diary to record daily pain ratings and opioid use.

Chronic Post-surgical Pain: Subjects will be contacted via telephone at 3- and 6-months following surgery to determine if CPSP is present utilizing a checklist based upon the IASP definition of CPSP (Appendix). If present, the BPI will be administered, and any opioid use recorded and checked against the PDMP. In addition, the PCS and PROMIS measures will be collected to evaluate the durability of CBT training effects.

2. Data Collection:

Data related to 72-hour post-operative pain and opioid use outcomes will be extracted from the EHR and opioid use data will be validated from PDMP entries; all other data will be sourced directly from the subject. These data are not existing at the time of submission of the IRB application. No tissue specimens will be collected or used in this study.

3. Genetic Testing:

Not applicable.

4. Use of Deception:

Not applicable.

5. Statistical Analysis:

Preliminary analysis of all outcome and baseline demographic variables will describe and test for differences in baseline measures between the groups. Adequacy of randomization will be evaluated by tests of differences between the intervention and usual care groups. These baseline comparisons will be based on t-tests or Wilcoxon rank sum tests for continuous variables, depending on the symmetry of the distributions; on logistic regression for

binary or ordinal variables; and on Poisson log-linear regression for count data. If imbalances are found at baseline, then the relevant variables will be treated as confounders in the post study analyses.

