For the second study objective, we expect that participants, who receive a MI intervention along with a validated computer-assisted CBT intervention for chronic pain (PAINTrainer) will demonstrate a significantly greater improvement in outcome variables from baseline vs those receiving usual care. The outcome variables will include change in the severity of pre-operative chronic pain, opioid use, and psychological risk factors (depression, anxiety, catastrophizing) for CPSP in the 4 weeks prior to surgery. Specifically, a mixed model analysis will be fit to the data using the Proc Mixed procedure in SAS.^{56,57} Residual modeling will be performed to check for significant violations in the distribution and constant variance assumptions and determine if variance stabilizing or normalizing transformations should be applied. Furthermore, sensitivity analyses will be run considering dichotomous versions of the outcome variables using multiple logistic regression.

For the third study objective, we will describe the effects of the CBT intervention on 72hr post-operative pain severity, and 3- and 6-month rates of CPSP in comparison to patients who received treatment-as-usual. A mixed effects model will be fit with Treatment Group (intervention and usual care) as a between subject factor and Time (72hr, month 3 and 6) as a categorical within-subjects factor. We will include as baseline covariates any factors that differ significantly between the groups at baseline or show significant relationships with the outcome.

Potential confounders (medical comorbidities, post-operative complications) will also be considered in the analysis.

The results from the mixed model analyses will be summarized by mean (SE) change from baseline for each group at each time point. The primary hypothesis will be evaluated at the alpha = 0.05 level and all contrasts/hypotheses will be considered exploratory and results will be interpreted with caution at alpha equal to 0.05 level. The primary goal will be to obtain reliable effect size estimates to inform larger studies. In that women are more likely to develop CPSP than men,^{8,16} sex as a biological variable will be considered as a possible moderator in all analyses.

RISK/BENEFIT ASSESSMENT:

1. Risks:

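### The pre-operative session text repeats the baseline assessments in the experimental group only, contradicting the schedule and study design; if followed, the Objective 2 between-group comparison would lack control data

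*Combined protocol and SAP*

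**What the plan says.** Study Procedures, 1. Detailed Description is introduced as the sequential account of every study contact. Its paragraph on the pre-operative study session says that "patients in the experimental group will meet with the study coordinator and baseline assessments will be repeated". The same paragraph adds the interview about the intervention, a 45-minute limit and the download of CBT use data. The section describes no pre-operative session for controls.

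Other parts of the document say or imply otherwise:

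- Study Design, on duration of participation: "Just prior to the surgery, subjects in both groups spend approximately 45minutes providing pre-operative data".
- Methods, 2. Group Modifications: "The only group modification with respect to measures is that only those in the intervention group will participate in the survey".
- Methods, 4. Administration of Surveys, schedule table: BPI, MEDD, PCS and PROMIS are all marked at T0. The footnote "subjects in treatment group only" is attached only to the row on CBT use, adherence and satisfaction.
- Methods, 1. Study Instruments: opioid dose is measured "during the study visit just prior to surgery and at the 3 and 6 months follow up", with no limit by arm.
- Objective 2 concerns outcomes "prior to surgery in comparison to 75 TKA patients randomized to treatment-as-usual".
- Study Design, opening paragraph: the risk factors are assessed "before and following the 4-week pre-surgical period and compared within and across subjects".
- Statistical Analysis, second objective: intervention participants "will demonstrate a significantly greater improvement in outcome variables from baseline vs those receiving usual care".

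**The concern.** Objective 2 compares change over the four weeks before surgery between the CBT arm and usual care, for pain severity, opioid use, depression, anxiety and catastrophizing. Control values at T0 are half of that comparison.

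The sentence that leaves controls out is the visit description that staff would work from. One study coordinator is responsible for all data collection (Resources section). The only other pre-surgical event described for controls after baseline is the usual-care class, which a nurse educator or physical therapist delivers.

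The loss could not be repaired afterwards. Under Study Procedures, 2. Data Collection, everything except the 72-hour outcomes comes directly from the subject, and a BPI, PCS or PROMIS score for the day before surgery cannot be collected once surgery has happened. What would remain is an uncontrolled pre-post change in the CBT arm, which cannot separate the intervention from regression to the mean or from the effect of approaching surgery.

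**Working it through.** No figure in the plan measures this point, so the check compares the texts and then asks what can be estimated.

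**Step 1. Who is assessed at T0?**

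| Place | T0 assessments given to |
|---|---|
| Detailed Description, pre-operative session | experimental group only |
| Study Design, duration of participation | both groups |
| Methods 2, Group Modifications | both groups (survey is the only difference) |
| Methods 4, schedule table | both groups (no arm restriction on BPI, MEDD, PCS, PROMIS) |
| Objective 2, Study Design opening, Statistical Analysis | both groups, by implication (between-group comparison) |

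One sentence stands against all the others.

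**Step 2. Does the stated participation time settle it?** The components come from Study Design.

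- Experimental: 1 h baseline + 9 h intervention + 0.75 h pre-operative + 1 h follow-up = 11.75 h. The plan says about 12 h, so this total is reproduced.
- Control with the T0 session: 0.5 + 4 + 0.75 + 1 = 6.25 h.
- Control without it: 0.5 + 4 + 1 = 5.5 h.

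The plan says about 7.5 h for controls. Neither sum matches, so the total does not show which text is right.

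**Step 3. What can be estimated under each reading?** Let G = 1 for the experimental group and 0 for control, and T = 1 at T0 and 0 at baseline. The cell means are

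mean = b0 + b1·G + b2·T + b3·G·T,

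and the Objective 2 contrast is

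b3 = (experimental T0 − experimental baseline) − (control T0 − control baseline).

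- T0 in both groups: four cells are observed and the design matrix has rank 4 of 4, so b3 is estimable.
- T0 in the experimental group only: the control T0 cell is empty and the rank is 3 of 4. The two baseline cells give b0 and b1. The experimental T0 cell then gives only the sum b2 + b3, so the effect of treatment cannot be separated from the effect of time.

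A mixed model does not help, because the whole cell is empty by design rather than partly missing. A comparison of T0 values alone fails for the same reason.

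**Step 4. Which outcomes would be lost in controls?** BPI, PCS, PROMIS depression and PROMIS anxiety come only from the subject and would be absent for all 75 controls, as would self-reported MEDD. Study Instruments has the PDMP queried at every timepoint as a check on self-report, so some control opioid data near T0 might be recovered. The schedule table, however, does not mark a PDMP review at T0.

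**The case against.** The strongest reply is that this is an obvious slip. Group Modifications answers the question directly, the schedule agrees with it, and Study Design states both groups outright. The stray sentence sits in a paragraph mostly about the intervention interview and the CBT use data, where naming the experimental group is natural. This reply stands as to what was intended. It does not remove the need to correct the sentence, because the Detailed Description is the section that presents itself as the complete account of study contacts.

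A reader might go further and infer that a one-arm pre-operative assessment was meant, since the sample-size paragraph speaks of a pre-post improvement with 75 participants. The documents do not support that. How a sample size was justified says nothing about who attends a visit; 75 is also simply the planned size of each arm, and the same paragraph goes on to recruitment per group. Whether that calculation suits a between-group comparison is a separate question and does not change with this sentence. The 45-minute figure is neutral too: the procedures give it for a session that includes the interview, and Study Design gives it for both groups.

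A reader might also infer that all five Objective 2 outcomes would be wholly lost in controls. That is too absolute for opioid use, because of the PDMP.

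**Conclusion.** The contradiction is real and should be corrected, though it is probably a drafting slip. Followed literally, the pre-operative session text leaves 0 of 75 controls with T0 values for BPI, PCS and both PROMIS scales, and with no self-reported MEDD. The Objective 2 difference in change could then not be estimated for the four outcomes that rest on self-report alone. For opioid use, at best a PDMP-based substitute would remain.

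This consequence depends on staff following that sentence rather than the schedule table. The documents do not show that they would, and the weight of the text favours assessment in both groups. The finding does not rest on any power calculation.

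**What to change.** In the pre-operative study session paragraph of the Detailed Description, replace the reference to patients in the experimental group with patients in both groups. In the same paragraph, state that the interview about the intervention and the download of CBT use data apply to the experimental group only. That brings the paragraph into line with Study Design, Group Modifications and the schedule table.

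The cost is an edit to one short paragraph. It adds no participant burden beyond the plan, since Study Design already gives about 45 minutes for pre-operative data in both groups.

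One related mismatch should be reconciled separately: Study Instruments has the PDMP queried at every timepoint, while the schedule table shows no PDMP review at T0. The edit above does not decide that question.
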